At the 2 year time point all subjects will have a 7444 mg egg white protein desensitization OFC on therapy. If the subject fails the 7444 mg egg white protein OFC on therapy, the subject will stop therapy and treatment options will be discussed with the subject. If the 7444 mg egg white protein OFC on therapy is passed, then the subject will be removed from therapy for 8-10 weeks and tested for sustained unresponsiveness with a second 7444 mg egg white protein OFC. If this 7444 mg egg white protein OFC off therapy is passed with successful consumption of an open feeding of egg, the subject will be considered to have achieved sustained unresponsiveness and advised to add egg to their diet on a regular basis and will be followed at 3 months by phone and 6 months in clinic to assess their egg diet history and reactivity to egg. If the subject fails the 7444 mg egg white protein OFC off therapy, further treatment options will be discussed with the subject.

ANNUAL LONG TERM FOLLOW-UP

All subjects will be contacted by telephone at years 3, 4, and 5 (through September 30, 2018) to assess consumption of egg in the diet.

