Appendix 1.A. Schedule of Events - Egg OIT Subjects

¹Performed only for subjects who pass the screening baked egg OFC.

² Egg OIT subjects will have initial escalation to at least 3 mg egg white solid on Day 1, return Day 2, return Day 3 if symptoms, return for dose escalation every 2 weeks until dose of 25 mg egg white solid is reached (12 mg for Egg OIT Assignment group).

³ Egg OIT subjects will have escalation visits every 2 weeks, unless epinephrine is administered as described in Section 6.4.1. Phone calls will occur 1 week after each escalation visit to assess dosing compliance and symptoms.

⁴ Only prior to any OFC, at baseline, a peak flow rate may be performed if spirometry results cannot be obtained.

⁵ Egg OIT subjects have 44 weeks maximum to reach highest tolerated dose ≥350 mg egg white solid. Subjects may escalate after 1 year OFC if they have not reached 2500 mg of egg white solid.

⁶For females of childbearing age.

⁷ In Clinical Research Center or monitored clinic setting.

- ⁸ Blood draws will not exceed 50 cc in a day but no more than 5cc/kg in a day or 9.5cc/kg in an 8 week period.

- ¹⁰ All mechanistic blood draws are performed prior to any oral food challenges. ¹⁰ If baked egg challenge is failed, the first 40 subjects will go directly to Egg OIT treatment. ¹¹ Daily home dosing for Egg OIT. Phone calls will occur monthly in between visits once maintenance is reached.

¹² Discontinue Egg OIT.

¹³ Only if desensitization challenge is passed, a repeat challenge off therapy in approximately 8-10 weeks will be performed.
¹⁴ Subjects who pass the sustained unresponsiveness oral food challenge will return for follow-up outlined in appendix 1-D
¹⁵ All subjects will be annually contacted by telephone starting 3 years after randomization, through a maximum of September 2018.

Procedure	Visit 00 Screening	Visit 00A Baseline ¹	Visit 01 ²	Visit 02 3 month (12 weeks)	Visit 03 6 month (24 weeks)	Month 9 Study Assessment ¹⁰	Visit 04 1 year (52 weeks)	Visit 05 16 month (68 weeks)	Visit 06 20 month (84 weeks)	Visit 07 2 year Desensitization ⁸ (104 weeks)	Visit 08 2 year sustained unresponsiveness ^{9,11} (112-114 weeks)	Visit F 03 3 year long term follow- up ¹²	Visit F 04 4 year long term follow up ¹²	Visit F 05 5 year long term follow up ¹²
Medical/Allergy History	х			x	X		х	x	x	х	Х			
Spirometry ³	x													
Physical Exam	х						х			х	Х			
Peak Flow Rate	х	х					Х			Х	х			
Pregnancy Test ⁴	x	х					х			x	х			

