Appendix 1.B. Schedule of Events - Baked Egg Subjects

¹Performed only for subjects who pass the screening baked egg OFC.

²Baked Egg subjects will come into the clinic on Day 1 to show what baked products will be used.

³ Only prior to any OFC, at baseline, a peak flow rate may be performed if spirometry results cannot be obtained.

⁴ For females of childbearing age.

⁵ Blood draws will not exceed 50 cc in a day but no more than 5cc/kg in a day or 9.5cc/kg in an 8 week period.

⁶ All mechanistic blood draws are performed prior to any oral food challenges.

⁷ Daily home dosing for Baked Egg. Telephone contacts will occur monthly in between clinic visits.

⁸ Discontinue Baked Egg therapy.

⁹ Only if desensitization challenge is passed, a repeat challenge off therapy in approximately 8-10 weeks will be performed ¹⁰ Subjects will return at month 9 to assess dosing compliance and any adverse events.

¹¹ Subjects who pass the sustained unresponsiveness oral food challenge will complete the follow-up outlined in Appendix 1-D

¹² All subjects will be annually contacted by telephone starting 3 years after randomization, through a maximum of September 2018.

Study Visit	Visit 00	Visit 02**	Visit 03**	Visit 04**	Visit 05**	Visit 06**	Visit 07**	Visit 08
Assessment*	Screening	3 month	6 month	(1 year)	16 month	20 month	(2 year)	~26 months
UniCAP	Х	Х	Х	Х	X	Х	Х	Х
Serum/Plasma	Х	Х	Х	Х			Х	Х
based assays								
T cells based	Х	Х	Х	Х			Х	Х
assays								
Basophil assays	Х	Х	Х	Х	X	Х	Х	Х
Epitope	Х			Х			Х	Х
microarray								
Estimated Blood	50cc	50cc	50cc	50cc	10cc	10cc	50cc	50cc
draw needed for								
Processing ¹								

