After Week 52: For subjects who discontinued dosing or withdrew from the study, the date of last dose is calculated as the minimum of the drug discontinuation date and the study withdrawal date minus one day. For subjects who did not discontinue dosing or withdraw, the date of last dose is calculated as the maximum of the date of last study visit and the day before their Year 2 desensitization OFC. Doses without dosing symptom logs that are to have occurred after 12 months but before the date of last dose are counted as doses that were administered with no symptoms. It is assumed that a dose would not occur on the day of the Year 2 desensitization OFC.

The number of expected doses will be calculated as days from the day after the Week 52 OFC through the discontinuation above. The percent of doses administered will be calculated as administered doses/expected doses.

Derived variables for mechanistic data are as follows:

1. % antigen-specific IgE = (antigen specific IgE / total IgE) X 100

Egg-specific IgG4/IgE: The egg specific IgG4/IgE ratio was calculated by converting IgG4 level from mgA/L to ng/mL and converting IgE level from kUA/L to ng/mL with the formula (IgG4 \times 1000) \div (IgE \times 2.4).

- 2. Activated Basophils = % CD63+ cells
- 3. Frequency and phenotype of egg-responsive T cells:

From 6 hour flow cytometry data:

a. CD154+CD3+CD4+ cell count (per million CD3+/CD4+)

b. CD154+CD3+CD4+(X)+, where X is IL-4, IL-13, IFN-g, IL-10, CCR4, CCR6, or CXCR5:

- 1. Cell count (per million CD3+/CD4+)
- 2. Frequency of CD154+CD3+CD4+, shown as a percentage
- 3. Delta (Egg-Media, CD3/CD28-Media).

c. CD154+CD25+CD127-CD3+CD4+ cell count (per million CD3+/CD4+)

From 18 hour data:

a. CD154+CD25+CD127-Foxp3+CD3+CD4+ cell count (per million CD3+/CD4+)

b. CD154+CD25+CD127-Foxp3+CD3+CD4+(X)+, where X is IFN-g, IL-10, CCR4, CCR6, or CCR9:

- 1. Cell count (per million CD3+/CD4+)
- 2. Frequency of CD154+CD25+CD127-Foxp3+CD3+CD4+, shown as a percentage
- 3. Delta (Egg-Media, CD3/CD28-media)

Effector regulatory ratio (Th2:Treg ratio):

This ratio is defined as CD154+CD3+CD4+IL4+ cell count (from 6h assay)/CD154+CD25+CD127-Foxp3+CD3+CD4+ cell count (at 18h), each adjusted with the same denominator (i.e., per million CD3+CD4+ cells).

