9.1.1 Solicited Adverse Events and Symptoms – Dosing Symptoms

Symptoms reported on the dosing symptom CRFs are considered treatment related for the purpose of analysis. Systemic symptoms are recorded as mild, moderate or severe.

The key outcome of interest is symptom free doses (defined as no oral pharyngeal or systemic symptoms). Exclusion of oral pharyngeal symptoms will also be considered. Other safety outcomes of interest include doses with moderate and/or severe reactions. Finally, doses requiring treatment will also be described with a focus on doses requiring epinephrine.

Symptoms will be reported per dose, per participant, and proportion of doses per participant. The latter will be calculated by dividing the number of doses with each symptom by the total number of doses the participant received. Formal comparisons of safety outcomes will occur on this measure although significance testing may be performed on other measures if warranted. Proportion of doses with symptoms per participant will be compared using the Wilcoxon Rank Sum test to do pairwise comparisons between treatment groups.

Finally, tables will be broken down by treatment, location, and timing (pre-Week 52 vs. post-Week 52) to illustrate potential dose level and temporal treatment effects.

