11.2 Immunoglobulin Results

Egg specific IgE, IgG4, and total IgE are measured at baseline, Week 12, Week 24, Week 52, Month 16, Month 20, Year 2, Month 26 and Month 30. Percent egg-specific IgE and IgG4/IgE ratio will be calculated as described in Section 3.3 above. Immunoglobulin results and changes from baseline will be reported at each of these timepoints by treatment group and by Year 2 sustained unresponsiveness status.

Change from baseline will be compared between treatment groups and by Year 2 sustained unresponsiveness status using the Wilcoxon Rank-Sum test to do pairwise group comparisons. A repeated measures model will be fit using the post-baseline timepoints except for the Month 30 visit (which is after the final OFC) and adjusted for baseline value, treatment or Year 2 sustained unresponsiveness status, and visit to assess any treatment effect or Year 2 sustained unresponsiveness effect on immunoglobulin measures. An appropriate covariance structure will be selected (with preference given to unstructured models). If there are too few subjects who have completed the Year 2 sustained unresponsiveness OFC to allow for a reasonable model fit, the model may be adjusted accordingly.

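### SAP 3.3 ends post-Week-52 dosing at the later of two dates, so off-therapy days enter the dose count of participants who pass the Year 2 OFC

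*SAP*

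**What the plan says.** SAP 3.3 (After Week 52) has two branches. Participants who discontinued dosing or withdrew get the earlier of two dates. Everyone else gets an end-of-dosing date "calculated as the maximum of the date of last study visit and the day before their Year 2 desensitization OFC". Two counts depend on that date:

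- Expected doses: "The number of expected doses will be calculated as days from the day after the Week 52 OFC through the discontinuation above".
- Administered doses: doses without a log that were due after 12 months and before that date "are counted as doses that were administered with no symptoms". Once routine log submission ends, only reactions and missed doses are logged, and SAP 3.3 assumes every unreported dose was taken without reaction.

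SAP 3.3 also assumes no dose on the day of the Year 2 OFC.

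In the protocol, a participant who fails the Year 2 OFC stops therapy. If the OFC is passed, "then the subject will be removed from therapy for 8-10 weeks and tested for sustained unresponsiveness" (6.4, Two Year OFC). At Visit 07 the Baked Egg schedule says "Discontinue Baked Egg therapy" (Appendix 1.B), and Appendix 1.A has the matching footnote for Egg OIT. Visit 08 follows at weeks 112-114: "Only if desensitization challenge is passed, a repeat challenge off therapy in approximately 8-10 weeks will be performed". Appendix 1.D adds an in-person visit, F 02, six months after the final OFC for those who pass it.

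The dose count is used in SAP 8.2 (compliance) and SAP 9.1.1 (proportion of doses with symptoms per participant): "The latter will be calculated by dividing the number of doses with each symptom by the total number of doses the participant received". That proportion is compared between groups by the Wilcoxon rank sum test.

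**The concern.** The Year 2 OFC is itself a study visit. Anyone who has it has a last visit on or after that day, so the maximum can never return the day before it. For a participant who passes, the last visit comes weeks or months after dosing ended. Nothing limits it to visits on therapy, and SAP 11.2 itself treats the six-month return as a visit when it fits its models to the post-baseline timepoints "except for the Month 30 visit (which is after the final OFC").

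Off-therapy days produce no logs, so under the no-log rule they look exactly like symptom-free dosing days. The symptom proportion is diluted and adherence is overstated. The dilution is also tied to efficacy: it is material only in those who pass the Year 2 OFC and largest in those who pass both challenges. An arm with more successes can look better tolerated through the derivation alone. The comparison of eOIT-Randomized with eOIT-Assigned is exposed in the same way, because the SAP expects less success in the assigned group.

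**Working it through.** The documents give no dose count to reproduce, so this is a day count on the nominal schedule, without visit windows.

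**Inputs.** Week 52 OFC = 52 × 7 = day 364. Year 2 OFC = 104 × 7 = day 728. Visit 08 = day 784 (week 112) or 798 (week 114). F 02 = Visit 08 + 182 days = day 966 or 980 (six months taken as 26 weeks). If the SAP's Month 30 label is used instead, F 02 is day 913. Illustrative assumptions not in the documents: a true symptomatic-dose rate of 10% and true adherence of 80%.

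**True exposure.** Days 365 to 727 = 363.

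**Formulas.**
- Counted days = last visit day − 364
- Excess = counted − 363
- Symptom rate as read = 10% × 363 / counted
- Pooled over both years, with about 363 Year 1 days = 10% × 726 / (726 + excess)
- Adherence as read = (0.80 × 363 + excess) / counted

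| Last visit | Counted | Excess | 10% reads (post-Week-52) | 10% reads (pooled) | 80% adherence reads |
|---|---|---|---|---|---|
| Visit 08, week 112 | 420 | 57 (15.7%) | 8.64% | 9.27% | 82.7% |
| Visit 08, week 114 | 434 | 71 (19.6%) | 8.36% | 9.11% | 83.3% |
| F 02, day 913 | 549 | 186 (51.2%) | 6.61% | 7.96% | 86.8% |
| F 02, day 966 | 602 | 239 (65.8%) | 6.03% | 7.52% | 87.9% |
| F 02, day 980 | 616 | 253 (69.7%) | 5.89% | 7.42% | 88.2% |

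A participant who fails the Year 2 OFC and has no later visit is counted to day 728, one day too many. If the cutoff is read strictly and the OFC day is left out, credited doses are two fewer in each row.

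**Arm level.** Take the planned sustained unresponsiveness rates (70% eOIT, 40% Baked Egg), the same true 10% in both arms, and only the F 02 excess. The arm mean is p × diluted rate + (1 − p) × 10%:

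- 602 days: 0.7 × 6.03 + 0.3 × 10 = 7.22% against 0.4 × 6.03 + 0.6 × 10 = 8.41%
- 616 days: 7.12% against 8.36%
- 549 days: 7.63% against 8.64%

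The artificial gap is 1.0-1.2 points post-Week-52. Pooled over both years it is 0.3 × (10 − 7.96) to 0.3 × (10 − 7.42), or 0.6-0.8 points. If only Visit 08 counts and 70%/40% are used as Year 2 pass rates, the gap is 0.3 × (10 − 8.64) to 0.3 × (10 − 8.36), or 0.4-0.5 points post-Week-52 and 0.2-0.3 pooled.

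**The case against.** Four points deserve weight.

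**The credit rule may exclude off-therapy days.** It covers doses that were due, and none is due after Visit 07. SAP 9.1.1 divides by doses received. On that reading the symptom proportions are right. But expected doses are still plain calendar days, so the error changes sign: a fully adherent participant who passes reads 363/420 to 363/434 = 84-86% adherent, or 363/616 to 363/549 = 59-66% if F 02 counts. The SAP's general assumption that unreported doses were taken also pulls against this reading.

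**The planned stop may count as a discontinuation.** Both documents use that word for it. The minimum rule would then apply and no off-therapy days would be counted. But everyone still on therapy stops at Year 2, so the branch for participants who did not discontinue, which refers to their Year 2 OFC, would cover almost no one.

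**The intent is visible.** If the last study visit meant the last one before the challenge, the maximum would correctly give the day before the OFC. The assumption of no dose on the OFC day points the same way. This is probably what was meant, but it is not written.

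**The effect on the test is usually small.** In simulations with 48 per arm and equal true rates (assumed Year 2 pass rates 80%/50%, sustained unresponsiveness 70%/40%, excess 64 days to Visit 08 or 246 to F 02), Wilcoxon rejection stayed near 5% with Visit 08 only and was about 5-8% with F 02 when rates were skewed across children. With unusually homogeneous rates (beta 4, 36), F 02 gave about 25% post-Week-52 and 12-13% pooled, while Visit 08 alone gave 6-7%. Participants with no symptoms cannot be diluted. An equal 10% in both arms is also only an illustration, since the protocol describes reactions to Baked Egg dosing as rare.

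These points limit the size and leave the direction open. They do not make the rule correct.

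**Conclusion.** The concern holds: the rule as written selects an off-therapy date for every participant who passes the Year 2 OFC. The firmer figure is the Visit 08 excess of 57-71 days (16-20%), because those dates exist at the primary analysis. The F 02 excess of 186-253 days (51-70%) needs that visit to have taken place and to count as a study visit. The 1.0-1.2 point arm gap also needs the literal crediting rule and equal true rates, so it is closer to a worst case than an expected bias.

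Three readings of the text give adherence overstated, adherence understated, or no error. A prespecified derivation should allow only one. What is affected is post-Week-52 and overall compliance, the symptom proportions and the tables split at Week 52. SAP 9 labels the dosing-symptom comparison exploratory. The primary endpoint, desensitization, SAE incidence, sample size and Year 1 dosing data are untouched. It should be fixed, but it does not threaten the trial's main conclusion.

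**What to change.** In SAP 3.3 (After Week 52), for participants who did not discontinue or withdraw, define the date of last dose as the day before the Year 2 desensitization OFC if it was done, and otherwise as the last on-treatment visit. End the expected-dose count on that same date and credit no dose after it. State that the planned stop at Visit 07 is not a drug discontinuation for this rule.

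Replacing the maximum with a minimum is not enough. If the last study visit were read as the last one before the challenge, the minimum would pick Visit 06 (week 84, day 588) and count 588 − 364 = 224 days instead of 363.

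The cost is one sentence in the SAP and one line of derivation code, with no change to data collection or study conduct. Symptom-free and adherence percentages may come out slightly less favourable.

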Starting at the maintenance dose achieved prior to the 1 year 7444 mg egg white protein OFC, subjects will begin the Clinical Research Center dosing scheme as outlined until 2500 mg of egg white solid is reached. Subjects will return for a supervised dose escalation in the clinic every 2 weeks. Subjects will be called 1 week after each dose escalation visit to assess for dosing compliance and dose reactions. Any dose escalation attempts may be postponed for 1-2 extra weeks based on clinical judgment. An escalation attempt must be made by 4 weeks. Subjects should withhold their daily home dose on the escalation day but should take all other prescribed medications. Note that the daily home dose should be taken as part of a meal. It is recommended that the dose be taken at a consistent time (within a 4 hour time period), and it is critical to take the dose every day. Doses should be separated by at least 12 hours. Subjects who require dosing reduction during the 2 week period will reset their 2 week escalation schedule to maintain the new dose for a 2 week period prior to attempting to escalate again. In year 2, when on maintenance dosing, the subject will return to the clinic every 4 months per the visit schedule with telephone contacts monthly to assess dosing compliance and any dosing symptoms.

Should significant systemic symptoms, which may include mild symptoms based on physician discretion or moderate or greater symptoms, are reported during the daily home dosing, the symptom/dosing algorithm will be followed to determine the best course of action. The appropriate treatment will depend on the type and number of symptoms. If significant symptoms occur consistently following 3 attempts to increase the daily oral dose in the Clinical Research Center or clinic with each attempt spaced 2-4 weeks apart, dosing escalation will be halted at the last tolerated dose, the subject continued on that dose as their maintenance dose. If subjects do not reach the 2500 mg maintenance dose 4 weeks prior to the end of study egg OFC, build-up will stop and the highest achieved dose will be maintained until the end of study egg OFC. Maintenance will be 4 weeks long prior to the end of study egg OFC.

Subjects will be allowed to take their other daily medications during the build-up and maintenance phases of the study (i.e., antihistamines, albuterol).

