3.3 Study Definitions and Derived Variables

The primary endpoint of the study will be the development of sustained unresponsiveness to a 7444 mg egg white protein OFC followed by open consumption of a whole egg, 8-10 weeks after discontinuing 2 years of daily Baked Egg or Egg OIT. OFCs will be conducted in a supervised setting and safety parameters will be carefully monitored. Individuals off therapy for 8-10 weeks, successfully demonstrating consumption of 7444 mg egg white protein during OFC without dose-limiting symptoms followed by an open feeding of a meal-sized portion of egg are considered successes; those not receiving the open feeding of a meal-sized portion of egg due to site error are also considered successes. Individuals who do not attempt this off therapy OFC or do not successfully consume 7444 mg egg white protein for this off therapy OFC will be considered "failures" with respect to this endpoint.

For the desensitization endpoint, all individuals with an SCD \geq 4444 mg egg white protein will be considered successes All others will be considered "failures" with respect to this endpoint.

For safety endpoints, the pre-defined secondary endpoint is the incidence of serious adverse events. Additional safety endpoints of interest include the incidence of adverse events related to dosing which will be estimated from the dosing symptom logs. For the first 12 months on therapy, or for the time until reaching the maximum maintenance dose if this occurs after 12 months, all dosing symptom logs are required to be submitted. Otherwise, only doses with reactions or missed doses have dosing symptom logs reported in the data system. All non-reported doses are assumed to have been successfully administered without reaction or treatment required. To estimate the number of doses administered, the following algorithm will be used:

Through Week 52: Date of last dose is calculated as the minimum of the completion date of the Week 52 OFC, the drug discontinuation date and the study withdrawal date minus one day. It is assumed that a dose would not occur on the day of Week 52 OFC.

The number of expected doses will be calculated as days from treatment initiation to date of last dose and the percent of doses administered will be calculated as administered doses/expected doses.

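### The After Week 52 rule in SAP 3.3 scores absent dosing logs as taken, symptom-free doses even for Egg OIT children whose every log is still required

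*SAP*

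**What the plan says.** SAP 3.3 sets up two reporting regimes for dosing logs. In the first, covering the first 12 months, "or for the time until reaching the maximum maintenance dose if this occurs after 12 months, all dosing symptom logs are required to be submitted". In the second, reporting is by exception: "Otherwise, only doses with reactions or missed doses have dosing symptom logs reported in the data system". The same paragraph then states: "All non-reported doses are assumed to have been successfully administered without reaction or treatment required".

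The After Week 52 algorithm in the same section turns this into a counting rule: "Doses without dosing symptom logs that are to have occurred after 12 months but before the date of last dose are counted". The sentence ends by saying that they "are counted as doses that were administered with no symptoms". Its only limits are 12 months and the date of last dose. It does not mention whether the child has reached the maximum maintenance dose.

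Both documents plan for some children to be below that dose after Week 52. SAP 4.1 and Protocol 6.4 have Egg OIT children who are below 2500 mg at the 1-year challenge resume build-up. For that phase Protocol 6.4 says: "Subjects will return for a supervised dose escalation in the clinic every 2 weeks".

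The counted doses feed two outputs. One is the percentage of doses administered (SAP 3.3, used in 8.2). The other is the per-participant symptom analysis in SAP 9.1.1: "Proportion of doses with symptoms per participant will be compared using the Wilcoxon Rank Sum test".

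**The concern.** Treating silence as a dose taken without trouble is sound only where silence is the expected report, which is the by-exception regime. Where a log is due for every dose, silence means that nobody knows what happened. The After Week 52 rule replaces the regime boundary (12 months or maximum dose, whichever is later) with a calendar boundary (12 months). It thereby carries the by-exception assumption into a period in which SAP 3.3 itself demands complete logs.

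The children concerned are Egg OIT participants, randomized or assigned, who are still building up in year 2. The Baked Egg group has no build-up to a maximum dose. For the affected children, a symptomatic dose with no log enters the denominator but not the numerator of the symptom proportion, and an untaken dose with no log counts towards adherence. Little else records daily home dosing: Protocol 5.5 notes that weighing the returned bulk powder cannot establish what was taken each day.

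**Working it through.** The plan states no figure that this point disputes. The check is a comparison of texts followed by an illustration.

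**Texts side by side**
- Reporting rule (SAP 3.3): full logging ends at the later of 12 months and the maximum maintenance dose.
- Counting rule (SAP 3.3, After Week 52): the default starts at 12 months.
- The two agree for any child at maximum dose by 12 months. They disagree for an Egg OIT child who reaches it later, over the whole interval between.

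**Length of that interval**
- The lowest accepted maintenance dose at the end of the first build-up is 350 mg (Protocol 6.4), which is dose 16. The 2500 mg dose is dose 25. That is 25 − 16 = 9 steps; at 2 weeks each, 18 weeks, or 18 × 7 = 126 doses. If the first step is taken at Week 52 itself, it is 8 × 2 = 16 weeks, or 112 doses.
- Build-up stops at the latest 4 weeks before the 2-year challenge (Protocol 6.4): 104 − 52 − 4 = 48 weeks, or 48 × 7 = 336 doses.
- Year 2 in total: 52 × 7 = 364 doses, approximately.

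**Effect on the symptom proportion**

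Let N = 364 be the year-2 doses, F the doses under full logging, s the true symptomatic share, and m the share of required logs missing at random. Assume that every symptomatic dose is reported in the by-exception period and that all doses were taken. The SAP rule loses s·m·F symptomatic doses from the numerator and leaves N unchanged:

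reported = s × (1 − m × F/N)

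Assumed inputs: s = 25%, constant (the prior egg OIT trial in Protocol 1.1 had 75% symptom-free doses in its year 1, so this is borrowed from another trial and another treatment year); m = 5% to 30% (not in the documents).

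| F | m | SAP rule | unknown doses excluded | all unknown doses symptomatic |
|---|---|---|---|---|
| 126 | 5% | 25% × (1 − 6.3/364) = 24.6% | 25% | (0.25 × 357.7 + 6.3)/364 = 26.3% |
| 126 | 30% | 25% × (1 − 37.8/364) = 22.4% | 25% | (0.25 × 326.2 + 37.8)/364 = 32.8% |
| 336 | 5% | 25% × (1 − 16.8/364) = 23.8% | 25% | (0.25 × 347.2 + 16.8)/364 = 28.5% |
| 336 | 30% | 25% × (1 − 100.8/364) = 18.1% | 25% | (0.25 × 263.2 + 100.8)/364 = 45.8% |

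Exclusion returns 25% because numerator and denominator shrink together when logs are missing at random.

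**Effect on adherence**

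If no missed dose is logged, the rule reports 100% administered. If none of the unlogged doses had been taken (the worst case), the true figure would be 1 − m × F/N: 98.3% and 89.6% for F = 126, and 95.4% and 72.3% for F = 336, at m = 5% and 30%.

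**The case against.** **The limit can be read from context.** In SAP 3.3 the general assumption follows directly on the by-exception sentence and may be meant only for that regime. That is a fair reading of the general paragraph. It does not rescue the After Week 52 sentence, which is what a programmer would implement and which carries no such limit.

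**SAP 6.5 provides a contingency.** It allows suitable methods if missing-data problems come to light. But the After Week 52 rule has already given these doses a value, so they would not show up as missing and nothing would trigger the contingency.

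**The stakes are modest.** This stands. SAP 9 calls the dosing-symptom comparison exploratory, although 9.1.1 speaks of formal comparisons on this measure. The primary, desensitization and serious-adverse-event endpoints do not use dosing logs.

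**Stronger readings a reader might infer.**
- That the between-group comparison is biased in favour of Egg OIT. The documents do not establish this. The missing-log rate is unknown. Escalating Egg OIT children are seen every 2 weeks with a call between visits, while Baked Egg children in year 2 have 4-monthly visits and monthly calls (Protocol 6.4). Closer follow-up in Egg OIT could offset or reverse the net direction, and no effect on a rank test has been shown.
- That the year-2 proportion shrinks by the full factor (1 − m), for example to 25% × 0.70 = 17.5%. That holds only within the full-logging segment, or if full logging lasts all year.
- That all 364 year-2 doses can be affected. This needs the maximum maintenance dose to mean 2500 mg only. Protocol 6.4 also accepts the last tolerated dose as maintenance after three failed escalation attempts.

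**Conclusion.** The inconsistency is real, and the rule as written is wrong for one identifiable set of children: Egg OIT participants still building up after 12 months. For them the algorithm turns a required but absent log into a taken, symptom-free dose. Their post-Week-52 symptom proportion is understated if any such dose had symptoms, and their adherence is overstated if any was not taken.

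The size is conditional. It is nil if no required log is missing. Under the stated assumptions it ranges from 0.4 percentage points (25% − 24.6%) to 6.9 points (25% − 18.1%) for an affected child. It would be larger if logs are skipped preferentially after reactions, and smaller if uneventful doses are the ones left unlogged. The point should be corrected, but it does not touch the trial's main conclusions.

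**What to change.** In SAP 3.3 (After Week 52):

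1. Limit the default to doses due after the later of 12 months and the date on which the child reached the maximum maintenance dose. State how that date is set for a child whose maintenance dose stays below 2500 mg, since the reporting rule depends on it.
2. For earlier doses with a required but absent log, treat the status as unknown. Remove them from both numerator and denominator of the symptom proportions, and from both parts of administered/expected. Removing them from administered doses alone would score each one as a missed dose, because expected doses are calendar days.
3. Report the number of required but absent logs by group.
4. Add a sensitivity analysis with the current rule (all taken, no symptoms) and the opposite extreme (all symptomatic for the symptom proportions, none taken for adherence). Exclusion is unbiased only if logs are missing at random, so the two extremes are needed to show how much rests on that.

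The cost is one clause in the SAP, one date comparison in the derivation program, and one extra table. Some Egg OIT denominators become smaller. If all required logs were submitted, no result changes.
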